5.1 Full Analysis Set (FAS)

The full analysis set (FAS) will include all subjects who receive at least one dose of IMP during the treatment period and for whom LDL-C values at baseline (baseline for efficacy endpoints) and at least one postdose visit (up until 2 days after final IMP administration) are observed.

5.2 Safety Analysis Set

The safety analysis set will include subjects who receive at least one dose of IMP during the treatment period.

5.3 Pharmacokinetic Analysis Set

The pharmacokinetic analysis set will include subjects who receive ETC-1002 and for whom time of blood collection for plasma drug concentration measurement is recorded.

5.4 Handling of Missing Data

In the primary analysis of the primary endpoint, when the LDL-C value at Week 12 is missing, the missing value will be imputed using the last value observed from after initial IMP administration up until 2 days after final IMP administration (last observation carried forward: LOCF).

In analysis of the percent change from baseline to Week 12 for secondary endpoints and of the proportion of subjects achieving the lipid management goals of LDL-C, missing values will be handled in the same manner as above. Missing values will not be imputed for sensitivity analysis and pharmacokinetic analysis.

Fasting lipid parameters will be handled as shown in the table below.

Condition	Fasting Lipid Parameters
Parameter to be used in analysis, irrespective of fasting condition	LDL-C (direct measurement)
Parameters to be used in analysis only when obtained under a fasting condition	LDL-C (Friedewald formula), HDL-C, non-HDL-C, TC, TG

6 Primary and Secondary Outcome Variables

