7.3.3 Documenting Reasons for Treatment Discontinuation

A subject may discontinue IMP for the reasons listed below: Only one reason for treatment discontinuation (primary reason) will be recorded in the source document and eCRF with the date of discontinuation and registered in the IWRs.

- Adverse event
 - Death
 - Worsening of underlying disease
 - Subject decides to discontinue because of annoyance or discomfort due to a nonserious AE which is not otherwise determined to be an undue hazard
 - Continuing IMP places the subject at undue risk as determined by the investigator or subinvestigator (eg, a safety concern that is related to IMP)
 - Serious adverse event
 - Other potentially IMP-related safety concerns or AEs
- Failure to meet randomization criteria
 - Assessed as ineligible based on the eligibility assessment at Week –1 (Visit S3) and Day 1 (Visit T1)

- Non-compliance with IMP (subjects with an IMP compliance rate of <80% between scheduled visits during the treatment period will be withdrawn from the trial. See [Section 6.1.2](#) for calculation of the IMP compliance rate.)
- Protocol deviations
 - Randomized by mistake
 - Revealed to have not met the inclusion criteria or fall under the exclusion criteria
 - Use of prohibited medications (including food and preference products) or prohibited therapies
 - Changes in the type and the dose and regimen of hypercholesterolemia drugs concomitantly used with the IMP (except for worsening of the underlying disease)
- Lost to follow-up
- Pregnancy (see [Section 10.3](#))
- Site terminated by sponsor
- Trial terminated by sponsor
- Withdrawal by subject's request (including withdrawal of consent by subject)
- Judgment by the investigator
- Other

If the subject discontinues IMP due to an AE, the investigator/subinvestigator, or other trial personnel, will make every effort to follow the event until it has resolved or stabilized. Follow-up procedures in [Section 7.3.2](#) must be followed.

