9.3 Handling of Missing Data for Primary Endpoint Analysis

In the primary analysis of the primary endpoint, when LDL-C at Week 12 is missing, the missing value will be imputed using the last value observed from after initial IMP administration until 2 days after final IMP administration (last observation carried forward: LOCF).

A mixed-effects model repeated measures analysis assuming missing at random will be performed using observed case data as sensitivity analyses.

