3.4 Trial Visit Window

Data observed at CRF Visit will be used at each analysis visit (but data at discontinuation will not be used in analysis). Data from unscheduled visits will not be used. Efficacy analysis will be performed using the data obtained up until 2 days after final IMP administration. In assessment of efficacy endpoints, baseline for fasting lipid parameters is defined as the mean of the values for Day 1 (Visit T1) and Week -1 (Visit S3). If only one value is obtained, that value will be used as baseline. For efficacy endpoints other than fasting lipid parameters, baseline is defined as the value for Day 1 (Visit T1). For safety endpoints, baseline is defined as the last data obtained prior to initial IMP administration in the treatment period.

4 Sample Size

Differences in the percent change in LDL-C from baseline to Week 12 in the ETC-1002 group versus the placebo group in non-Japanese phase 3 trials were -18.1% and -17.42% in trials in statin tolerant subjects and -21.41% and -28.45% in trials in statin intolerant subjects. Based on the results, the difference between the ETC-1002 group and the placebo group in the subjects with statin tolerance was assumed to be 17% , and the difference between the ETC-1002 group and the placebo group in the subjects with statin intolerance was assumed to be 25% . For the present trial it was assumed that the percentage of statin intolerant subjects enrolled would be 20% and that the difference in the endpoint between the ETC-1002 group and the placebo group would be 19% in the overall trial population. Based on the results of the phase 3 trials, assuming a difference of 19% with standard deviation of 25% between the ETC-1002 groups and the placebo group in the percent change in LDL-C from baseline to Week 12, 38 subjects per group are required to achieve a power of 90% or higher in a two-tailed test with a 5% significance level. Assuming a withdrawal rate of 12.5% , the target number of subjects to be randomized was set at 44 per group.

5 Statistical Analysis Datasets

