6.2 Secondary Outcome Variables

- Percent change in HDL-C, non-HDL-C, TC, TG, apo B, hsCRP, and HbA1c from baseline to Week 12
- Proportion of subjects whose LDL-C value achieves the lipid management goals based on risk assessment (<100 mg/dL [history of coronary artery disease or heterozygous familial hypercholesterolemia], <120 mg/dL [high risk], or <140 mg/dL [intermediate risk]) and the proportion of subjects whose LDL-C value achieves <70 mg/dL at Week 12

7 Disposition and Demographic Analysis

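### LOCF for the LDL-C goal proportion credits some subjects who stopped drug early as Week 12 successes, and no planned analysis counts them as not at goal

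*SAP*

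**What the plan says.** For the primary endpoint, SAP 5.4 states that "the missing value will be imputed using the last value observed from after initial IMP administration", with a cut-off 2 days after the final dose. It then extends the rule to the secondary percent changes and to the proportion achieving the lipid management goals: "missing values will be handled in the same manner as above".

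SAP 3.4 narrows what can be carried forward. Efficacy analysis uses "data obtained up until 2 days after final IMP administration". Values come from scheduled CRF visits, "but data at discontinuation will not be used in analysis", and unscheduled visits are not used.

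The protocol does not extend LOCF this far. Protocol 9.3 opens with "In the primary analysis of the primary endpoint, when LDL-C at Week 12 is missing", and protocol 9.4.1.3 gives no missing-data rule for the proportions.

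There are two binary endpoints. One is the risk-based goal (<100, <120 or <140 mg/dL). SAP 6.2 lists the other separately as "the proportion of subjects whose LDL-C value achieves <70 mg/dL at Week 12". SAP 5.4 names only the lipid management goals.

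SAP 8.2 analyses both proportions by a Cochran-Mantel-Haenszel test stratified by statin response. It repeats this on observed cases at each visit, including Week 12. No analysis treats a missing Week 12 value as not at goal.

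**The concern.** The endpoint is being at goal at Week 12. Every subject must be above goal at Week -5 and Week -1 (protocol 5.2.1). Protocol 4.2 reports that LDL-C had fallen by Week 2 to 4 in the non-Japanese phase 3 trials. A value from an early visit can therefore already be below goal, and LOCF will let it stand for Week 12.

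Missing Week 12 data will often mean that the drug was stopped. Subjects are withdrawn for compliance below 80% between visits (protocol 6.1.2). Protocol 7.3.3 also lists adverse events, changes to the background lipid drugs and "Use of prohibited medications (including food and preference products) or prohibited therapies". Fed-state sampling should not add missing values, because SAP 5.4 uses directly measured LDL-C irrespective of fasting and SAP 8 makes it the default.

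What is at stake is how the responder rates and their differences from placebo are read. Part of each rate may come from subjects who were no longer taking the drug at Week 12, and nothing in the planned output shows how large that part is.

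**Working it through.** **Planning figures.** The documents give no expected goal rate and no power for the proportions, so the plan offers no figure for this endpoint to reproduce. The primary-endpoint inputs used below do reproduce:
- With a difference of 19, SD 25 and two-sided 5%, a two-sample t-test has power 0.897 at 37 per group and 0.905 at 38. The plan states 38.
- 38/0.875 = 43.4, so 44 are randomized per group.
- The pooled difference is 0.8×17 + 0.2×25 = 18.6, stated as 19.

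**Formulas.** In one arm of the FAS, let d be the share with no Week 12 LDL-C, p the at-goal rate among those observed, and q the at-goal share among the last values of those missing.
- LOCF rate = (1−d)p + dq
- Observed-case rate = p
- Non-responder imputation (NRI) rate = (1−d)p
- LOCF minus NRI = dq, which is never negative and never exceeds d
- For the active minus placebo difference, LOCF minus NRI = dA·qA − dP·qP

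**Ceiling per arm.** With d = 12.5%, LOCF adds at most 12.5 points, or 0.125×44 = 5.5 subjects.

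**Equal missingness.** The following are assumptions, not in the documents. Percent change is Normal with SD 25 and mean 0 on placebo or −19 on active. The reduction r needed to reach goal is 10% to 30%. Missingness is 12.5% in both arms, and q = p. The at-goal probability is Φ((−r−mean)/25). For r = 20 this gives Φ(−0.80) = 0.212 on placebo and Φ(−0.04) = 0.484 on active.

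| r | LOCF: placebo, active, difference | NRI: placebo, active, difference | LOCF − NRI, difference |
|---|---|---|---|
| 10% | 34.5, 64.1, 29.6 | 30.2, 56.1, 25.9 | +3.7 |
| 20% | 21.2, 48.4, 27.2 | 18.5, 42.4, 23.8 | +3.4 |
| 30% | 11.5, 33.0, 21.5 | 10.1, 28.9, 18.8 | +2.7 |

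Entries are percent or points, computed before rounding. LOCF adds 4.1 to 8.0 points to the active rate and 1.4 to 4.3 to the placebo rate.

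**Unequal missingness** (r = 20%, LOCF difference 27.2 points):

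| Placebo missing | Active missing | NRI difference | LOCF − NRI |
|---|---|---|---|
| 5% | 20% | 18.6 | +8.6 |
| 12.5% | 5% | 27.4 | −0.2 |
| 20% | 5% | 29.0 | −1.8 |

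The sign changes when dP/dA exceeds qA/qP = 0.484/0.212 = 2.3.

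**What the observed-case analysis can show.** If q = p, the LOCF rate is (1−d)p + dp = p, which is the observed-case rate. The two then agree exactly whatever d is, so their agreement says nothing about the distance to NRI.

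**The case against.** A reader might infer that LOCF counts early leavers in general as at goal. It does not. Only those whose last scheduled on-treatment value was below threshold are credited, and the rest count as failures.

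A reader might also infer that the treatment difference must be biased upward. The documents do not support that either. The difference rises only if dA·qA exceeds dP·qP. It is unchanged if the two are equal and falls if placebo loses enough more subjects.

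The stronger defence is that the plan is consistently on-treatment. The 2-day cut-off governs the efficacy data, the LOCF rule and the FAS, which requires that LDL-C values at baseline and "at least one postdose visit (up until 2 days after final IMP administration) are observed". NRI answers a different question, in which missing Week 12 data count as failure. The documents define no estimand, so inflation can be claimed only relative to that question. This stands, and the conclusion is worded accordingly.

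The size is also modest. A gap of 3.7 points is 0.037×44 = 1.6 subjects. If leavers are at goal half as often as completers, which is plausible for poor compliers, the equal-missingness gap halves to about 1.3 to 1.9 points. Missingness within the FAS may be below 12.5%, because subjects with no post-dose LDL-C are excluded.

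The observed-case analysis is a partial check, since it credits no leaver. But it removes leavers from the denominator instead of counting them as failures, so it cannot take the place of NRI.

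On <70 mg/dL, SAP 6.2 puts both thresholds in one bullet and SAP 8.2 treats them alike, so LOCF was probably meant for both. Taken alone, this is a gap in wording.

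**Conclusion.** The point holds as a minor one. Some subjects who stopped drug early will be recorded as at goal at Week 12, and no planned analysis shows the result with them counted as not at goal. Relative to that alternative, LOCF can only raise an arm's rate or leave it unchanged. The effect on the difference from placebo is about 3 to 4 points with 12.5% missing in each arm, 8.6 points if active loses far more subjects, and −1.8 points in the example where placebo does.

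These sizes rest on the Normal model, the assumed reductions needed to reach goal, the assumed missing shares, and leavers being at goal as often as completers. Only the difference of 19, the SD of 25 and the 12.5% withdrawal come from the plan.

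The primary conclusion is not touched. The closed testing procedure covers only the primary endpoint (protocol 9.4.1.4, SAP 8.1.1), and no key secondary endpoint is defined (protocol 9.4.1.2).

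**What to change.** In SAP 5.4 and 8.2, name both binary endpoints, the risk-based goal and <70 mg/dL. State that an FAS subject with no valid Week 12 LDL-C is counted as not at goal. Keep LOCF and the planned Week 12 observed-case analysis as supportive. At minimum, report the non-responder analysis beside the LOCF result for both endpoints, and say which missing-data rule applies to <70 mg/dL.

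The cost is a sentence or two in the SAP and one more version of two tables, with no new data. The downside is lower stated responder rates, and conservatism if missingness is unrelated to response.

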6.1 Primary Outcome Variables

Percent change in LDL-C from baseline to Week 12

6.2 Secondary Outcome Variables

- Percent change in HDL-C, non-HDL-C, TC, TG, apo B, hsCRP, and HbA1c from baseline to Week 12
- Proportion of subjects whose LDL-C value achieves the lipid management goals based on risk assessment (<100 mg/dL [history of coronary artery disease or heterozygous familial hypercholesterolemia], <120 mg/dL [high risk], or <140 mg/dL [intermediate risk]) and the proportion of subjects whose LDL-C value achieves <70 mg/dL at Week 12

7 Disposition and Demographic Analysis

7.1 Subject Disposition

The number of subjects who provide informed consent, the number of screening failures, and the number and percentage (using the number of subjects who provide informed consent as the denominator) of IMP-treated subjects and discontinued subjects and the reasons for discontinuation [REDACTED] will be summarized.

The number of randomized subjects and the number and percentage (using the number of randomized subjects as the denominator) of subjects who receive IMP, who complete the trial, and who withdraw from the trial and the reasons for withdrawal in the treatment period will be summarized by treatment group (by dose and overall for ETC-1002).

For subjects who are randomized, the number and percentage of subjects included in each analysis set will be summarized by treatment group (by dose and overall for ETC-1002).

The same analysis will also be performed by the randomization stratification factor (statin response).

7.2 Demographic and Baseline Characteristics

For each analysis set, descriptive statistics (mean, standard deviation, median, minimum, and maximum, the same hereinafter) of age, height, body weight, and BMI and frequency distributions of categorized age (<65 years, \geq 65 years), sex, race, ethnicity, country, presence/absence of medical history, and presence/absence of complications will be summarized by treatment group (by dose and overall for ETC-1002). For body weight, values at screening will be used.

The same analysis will also be performed by the randomization stratification factor (statin response).

7.3 Baseline Disease Evaluation

For the FAS and safety analysis set, frequency distributions of presence/absence of hypercholesterolemia, presence/absence of familial hypercholesterolemia, risk assessment (history of coronary artery disease or familial hypercholesterolemia, high risk, or intermediate risk), presence/absence of diabetes mellitus, and statin response (statin tolerance/statin intolerance) will be summarized by treatment group (by dose and overall for ETC-1002).

The same analysis except for statin response will also be performed by the randomization stratification factor (statin response).

For subjects with statin intolerance in the FAS and safety analysis set, frequency distributions of presence/absence of statin intolerance-associated symptoms (muscle impairment, hepatic impairment, renal impairment, cognitive impairment, or other) and presence/absence of causal medication for statin intolerance (atorvastatin calcium trihydrate, fluvastatin sodium, pitavastatin calcium, pravastatin sodium, rosuvastatin calcium, or simvastatin) will be summarized by treatment group (by dose and overall for ETC-1002).

7.4 Treatment Compliance

For the FAS and safety analysis set, frequency distributions of IMP compliance rate ($<70\%$, $\geq70\%$ to $<80\%$, $\geq80\%$ to $<90\%$, or $\geq90\%$) in the treatment period will be summarized by treatment group (by dose and overall for ETC-1002). The IMP compliance rate will be calculated using the following formula.

$$\text{IMP compliance rate (\%)} = \frac{\text{Actual number of days of taking 3 tablets of the IMP}}{\text{Date of final IMP administration} - \text{Date of initial IMP administration} + 1} \times 100$$

The same analysis will also be performed by the randomization stratification factor (statin response).

For the FAS, the number and percentage of subjects who do not change the type and the dose and regimen of hypercholesterolemia drugs, which are mandatory concomitant medication in this trial, throughout the treatment period will be summarized by treatment group (by dose and overall for ETC-1002).

The same analysis will also be performed by the randomization stratification factor (statin response).

7.5 Prior and Concomitant Medications

For the FAS, frequency distributions of medications used prior to or during the treatment period by drug class and by preferred term in World Health Organization Drug Dictionary (WHODD) version B3 September 2020 will be summarized by treatment group (by dose and overall for ETC-1002).

For the FAS, frequency distributions of presence/absence of statin use or ezetimibe use will be summarized by treatment group (by dose and overall for ETC-1002). The preferred terms for statins and ezetimibe are shown in [Appendix 4](#).

The same analysis will also be performed by the randomization stratification factor (statin response).

7.6 Protocol Deviations

For subjects who are randomized, frequency distributions of presence/absence of the following deviations recorded in the CRF will be summarized by treatment group (by dose and overall for ETC-1002).

- Dosing
- Inclusion/exclusion criteria
- Met withdrawal criteria but was not withdrawn
- Procedural deviations (Affecting primary outcome variables)

- Prohibited concomitant medications

The same analysis will also be performed by the randomization stratification factor (statin response).

8 Efficacy Analysis

Efficacy analysis will be performed for the FAS using values measured by the central laboratory. For LDL-C, values obtained by direct measurement will be used unless otherwise stated. Efficacy analysis for the treatment period is described below.

8.1 Primary Efficacy Endpoint

The primary efficacy endpoint is the percent change in LDL-C from baseline to Week 12.

8.1.1 Primary Efficacy Analysis

For the primary analysis of the primary endpoint, analysis of covariance will be performed using treatment group and statin response (statin tolerance/statin intolerance), the randomization stratification factor, as factors and baseline value of LDL-C as a covariate. The overall Type I error rate will be controlled by performing comparison versus the placebo group starting from the highest ETC-1002 dose group by a closed testing procedure at a two-sided significance level of 0.05. Baseline is defined as the mean of the LDL-C values for Day 1 (Visit T1) and Week -1 (Visit S3). If only one value is observed, that value will be used as baseline. In the analysis of covariance described above, the least squares mean for each treatment group and the differences in the mean of the least squares between each ETC-1002 group and the placebo group, together with the two-sided 95% confidence intervals, will be calculated. The same analysis will also be performed for the percent change in LDL-C from baseline at each visit (Week 2, Week 4, Week 6, Week 8, and Week 12) using measured values (Observed case, OC).

The percent change in LDL-C from baseline to Week 12 will be tested using a contrast for low-dose saturation (L-end), medium-dose saturation (M-end), and linear (L-end: 3-1-1-1, M-end: 5 1-3-3, Linear: 3 1-1-3) to investigate the dose-response relationship between placebo and ETC-1002 low dose, medium dose, and high dose. Multiplicity will not be considered in the analyses for dose-response relationship.

8.1.2 Sensitivity Analyses

A mixed-effects model repeated measures (MMRM) analysis assuming missing at random will be performed using OC data to calculate the least squares mean for each treatment group and the differences in the mean of the least squares between each ETC-

1002 group and the placebo group, together with the two-sided 95% confidence intervals, for the percent change in LDL-C from baseline at each visit (Week 2, Week 4, Week 6, Week 8, and Week 12). The MMRM model will include treatment group, the randomization stratification factor, visit, and treatment group-by-visit interaction as factors and baseline and baseline-by-visit interaction as covariates using an unstructured error covariance matrix. The Kenward-Roger method will be used to calculate the degree of freedom. If the MMRM procedure fails to converge in variance component estimation, the following error covariance structures will be used in the order of 1) heterogeneous toeplitz, 2) heterogeneous autoregressive of order 1, and 3) heterogeneous compound symmetry, and the first structure to yield convergence will be used. If a structure other than unstructured is selected, a sandwich estimator of standard error will be used.

8.1.3 Technical Computational Details for Primary Efficacy Analysis

Analysis of covariance, which is the primary analysis, will be performed using the following SAS code.

```
proc mixed;  
  class treatment strata;  
  model pchange = treatment strata baseline / solution;  
  lsmeans treatment / pdiff=control('placebo') cl;  
  run;
```

Analysis using a contrast to investigate the dose-response relationship will be performed using the following SAS code.

```
proc mixed;  
  class treatment strata;  
  model pchange = treatment strata baseline / solution;  
  lsmeans treatment / pdiff=control('placebo') cl;  
  contrast 'L-end' treatment 3 -1 -1 -1;  
  contrast 'M-end' treatment 5 1 -3 -3;  
  contrast 'Linear' treatment 3 1 -1 -3;  
  run;
```

MMRM analysis as sensitivity analysis will be performed using the following SAS code.

```
proc mixed;
```

```
class treatment strata visit subjid;  
model pchange = treatment visit baseline treatment*visit baseline*visit strata /  
ddfm=kr;  
repeated visit / type=un subject=subjid;  
lsmeans treatment*visit / diff cl;  
run;
```

